12.1 Data Reporting

12.1.1 Method

The ODQ will collect, manage, and perform quality checks on the data for this study.

12.1.2 Responsibility for Data Submission

Investigative sites within DF/HCC or DF/PCC are responsible for submitting data and/or data forms to the ODQ according to the schedule set by the ODQ.

12.2 Data Safety Monitoring

The DF/HCC Data and Safety Monitoring Board (DSMB) will review and monitor study progress, toxicity, safety and other data from this study. The board is chaired by a medical oncologist from outside of DF/HCC and has external and internal representation. Information that raises any questions about participant safety or protocol performance will be addressed by the Overall PI, statistician and study team. Should any major concerns arise, the DSMB will offer recommendations regarding whether or not to suspend the study.

The DSMB will meet twice a year to review accrual, toxicity, response and reporting information. Information to be provided to the DSMB may include: participant accrual; treatment regimen information; adverse events and serious adverse events reported by category; summary of any deaths on study; audit results; and a summary provided by the study team. Other information (e.g. scans, laboratory values) will be provided upon request.

13. STATISTICAL CONSIDERATIONS

13.1 Study Design/Endpoints

This is an open label phase 2 trial that randomizes 45 mCRPC patients (2:1 ratio) to radium-223 plus pembrolizumab combination therapy or to radium-223 monotherapy. The primary objective is to compare the increase in immune CD8+ and CD4+ T cell infiltration levels from baseline to 8 weeks on treatment between the two treatment arms.

Primary Endpoint:

Difference in tissue immune cell (e.g., CD4+/8+T) infiltration in the bone metastasis biopsy specimens from baseline to 8 weeks on treatments in both the combination and monotherapy arms.

Secondary Endpoints:

- Safety and Tolerability: grade 3 or higher adverse events that are considered treatment related according to NCI CTCAE (version 4.0)
- Progression-free survival (PFS): is defined as the time from the first dose of study drug to the earlier of the first documentation of definitive disease progression [as

defined by Response Evaluation Criteria in Solid Tumors (RECIST version 1.1) and PCWG2] or death due to any cause. Participants alive without disease progression are censored at date of last disease evaluation

• Overall survival as defined in 11.1.8

Exploratory Endpoints:

- Clinical-based endpoints
 - Changes in PSA
 - PSA response: defined as decline ≥50% from baseline to 12 weeks of therapy and which has been confirmed with a second PSA at ≥ 3 weeks later
 - Time to PSA progression as defined in 11.1.9
 - Time to normalization of alkaline phosphatase (if initially elevated)
 - Time to decrease in alkaline phosphatase (if initially elevated)
 - Symptomatic skeletal events (SSEs): Rate of SSEs and time to first SSE
 - Changes in osteoblastic activity on bone scan (assessed using the quantitative SPECT/CT)
 - Changes in quality of life, pain, and analgesic use, and time to introduction of analgesics
 - Immune-based endpoints
 - Quantify the CD8, CD4, and FoxP3+ CD4 (Treg) cell infiltration in the bone biopsy specimens, and to subsequently quantify the CD8/Treg and CD4/Treg ratios
 - Change in circulating T cell clonality
 - Induction of IgG antibody response
 - Changes in PD-L1 expression and co-regulation of other immune checkpoints such as TIM-3, LAG-3, and PD-L2
 - Changes in immunosuppressive cell populations and cytokines (e.g., MDSCs, Tregs, TGF-β, and iNOS)
 - Change in serum chemokines: (e.g., CXCL9, CXCL10)

- Changes in soluble PD-L1 ([name] Lab assay)
- Genomic-based endpoints
 - Correlation of DNA damage repair (DDR) mutations in baseline tumor samples and circulating cf-DNA with progression-free survival (PFS) on radium-223 ± pembrolizumab.
 - DDR encompasses genes such as BRCA1, BRCA2, FANCA, ATM, PALB2, HDAC2 and CK2
 - PFS will be defined as time from randomization to:
 - Appearance of 2 or more new bony lesions compared to baseline, confirmed on a repeat bone scan ≥6 weeks later
 - Appearance of new soft tissue lesions on CT/MRI or progression of existing ones per RECIST 1.1 criteria
 - Death from any cause
 - Prevalence of mutations in DDR genes in tissue or cf-DNA in patients with metastatic CRPC treated with Ra-223
 - Incidence of novel genomic alterations detected at the time of progression as mechanisms of treatment resistance
 - Impact of baseline cf-DNA tumor purity (defined as percentage of tumor derived circulating DNA; high: >7.5% vs. low: \leq 7.5%) on subsequent PFS
 - Change in tumor purity from baseline to weeks 5 and 13
 - Impact of change in tumor purity at 13 weeks (increased/stable vs. decreased compared to baseline) on PFS
 - PSA response (defined as PSA decline ≥50% compared to baseline) and overall survival (OS: defined as time from randomization to death from any cause) in patients with and without DNA repair mutations on radium-223 ± pembrolizumab.

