10. STUDY CALENDAR

All baseline evaluations are to be conducted within 42 days prior to treatment initiation.

Assessments must be performed prior to administration of any study agent. On-study assessments should be administered within 72 hours of the protocol-specified date but prior to study drug administration. Imaging assessments may have a window of +/- 7 days but must remain on schedule even if doses are being held for toxicity or other reasons.

For participants on Arm A, if pembrolizumab is discontinued for toxicity, visits and assessments will then follow the schedule for Arm B. If radium-223 is discontinued, visits and assessments will be every 3 weeks at the time of the pembrolizumab dosing. The radium-223 visits on Arm A will be discontinued and not considered a protocol violation. The quality of life questionnaires and immune studies will be done on the pembrolizumab visit closest to their required visit if they had stayed on radium-223 (e.g., will be done on week 7 instead of week 8). Imaging assessments will remain the same on an every 12 week basis.

Study Calendar	Pre- Study ^A	Wk 1	Wk 4 (Arm A only)	Wk 5	Wk 7 (Arm A only)	Wk 8	Wk 9	Wk 10 (Arm A only)	Wk 13+ (R)	End of Treatment ^S
Informed consent	Х									
Demographics	Х									
Medical history	Х									
Concurrent meds	Х	Х	Х	Х	Х	Х	Х	Х	Х	
Physical exam ^B	Х	Х	Х	Х	Х		Х	Х	Х	Х
Vital signs ^C	Х	Х	Х	Х	Х		Х	х	Х	Х
Height	Х									
Weight	Х	Х	Х	Х	Х		Х	х	Х	Х
ECOG Performance status	Х	Х	Х	Х	Х		Х	Х	Х	Х
CBC w/diff, plts ^D	Х	Х	Х	Х	Х		Х	Х	Х	Х
Serum chemistry ^E	Х	Х	Х	Х	Х		Х	Х	Х	Х
Testosterone	Х									
PSA ^F	Х	XF		Х			Х		Х	Х
TSH, Free T4 ^G	Х		х	Х					х	
PT/INR, PTT ^H	Х									
EKG	Х									
Pembrolizumab ^I (Arm A only)		х	Х		Х			х	Х	
Radium-223 ^J		Х		Х			Х		$(X)^{J}$	
Adverse event evaluation ^K		Х	х	Х	х		Х		х	Х
Radiologic evaluation & Tumor measurements ^L	X								X^L	
Correlative immune studies ^M		Х		Х			Х		X*	
Bone biopsy ^N	Х					Х				
cfDNA ⁰		Х		Х					Х	
FACT-P Survey ^P		Х		Х			Х		Xo	X
Brief Pain Inventory ^P		Х		Х			Х		Xo	Х
Analgesic Diary ^P		Х		Х			Х		Xo	Х
Follow-up ^Q										XQ

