A: All baseline evaluations are to be conducted within 42 days prior to treatment initiation. In the event that the participant's condition is deteriorating, laboratory evaluations should be repeated within 48 hours prior to initiation of the next cycle of therapy. D1 labs and assessments do not need to be performed if have been done within 72hrs prior to study drug dosing. C1D1 labs do not need to re-meet eligibility criteria but do need to meet criteria as detailed in Section 5.2.1.

B: Physical examination should include general description of participant, head, eyes, and throat, chest, abdominal, extremities, neurologic, skin, and lymph node examination. Any other evaluation is up to the discretion of the practitioner. It will not be considered a violation if the exam is not described as outlined here. Patient will be seen in clinic the day of any study drug infusion (e.g., radium-223 and/or pembrolizumab)

C: Vital signs included blood pressure, heart rate, respiratory rate, body temperature

D: CBC with differential should be done before each dose of radium-223 and pembrolizumab.

E: Serum chemistry to include full CMP with sodium, potassium, chloride, bicarbonate, BUN, creatinine, glucose, calcium, albumin. Liver function tests to include AST, ALT, total bilirubin and direct bilirubin, alkaline phosphatase.

F: PSAs should be done at baseline, week 1 day 1 (per treating investigator's discretion), every 4-6 weeks on therapy, and at study end.

G: TSH, Free T4 to be done a baseline, week 4 (week 5 for arm B), week 13, and then approximately every 12 weeks.

H: Coagulation factors to include PT and INR.

I: Pembrolizumab will be given by IV every 3 weeks (+/- 3 days) in Arm A only.

J: Radium-223 will be given by IV every 4 (+/- 7 days) weeks for a maximum of 6 doses.

Arm A: Radium-223 will be held after 3 doses. It may be restarted (to complete the final doses up to a maximum of 6 from study start) when there is progressive disease in bones as long as there is no new visceral disease.

Arm B: Radium-223 will be given as per standard of care monthly for 6 months in a row without breaks except for toxicity/intolerance as detailed in Section 6.2.

K: Adverse events will be monitored continuously

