L: Diagnostic CT chest and CT or MRI of the abdomen and pelvis and bone scan including SPECT/CT should be obtained at baseline and every 12 weeks (+/- 7 days). (NOTE: SPECT/CT will be done only at DFCI.) Scans should remain on an every 12 week schedule (+/- 7 days) even if dose delays occur.

M*: Correlative immune studies: will be obtained and transported overnight at room temperature to the [name] Lab at UCSF. Samples for immune studies will be done at week 1 (pre-dose), week 5, week 9, week 13, week 21 and at the time of progression for those patients still on study.

N: Bone biopsy: archival tissue is permitted for baseline analysis. IR guided bone biopsy will be done at week 8 (+3 weeks) after the second dose of radium-223. If the second dose cannot be given for safety reasons, biopsy should still be performed within the window detailed here.

O: Blood samples for cell free DNA (cf-DNA) will be performed at treatment initiation (week 1, pre-dose), on treatment (week 5 and 13), and at time of progression.

P: Quality of life, pain and analgesic use will be measured via the FACT-P (Appendix B), Brief Pain Inventory (Short Form) (Appendix C), and analgesic diary (Appendix D) prior to treatment, at week 5, 9, then every 6-8 weeks after week 9 (as schedules differ between the two arms), and at treatment progression/off study visit.

Q: After progression/treatment discontinuation, follow the participant for survival, receipt of next line therapies, and post-treatment SSEs every 6 months until death or 2 years after treatment discontinuation.

R: Arm A study assessments will continue based on the same schedule as detailed for weeks 1-13 when pembrolizumab is given alone (e.g., visits, labs, assessments every 3 weeks only). If radium-223 is resumed upon progression, assessment schedule and radium-223 + pembrolizumab dosing will resume based on the schedule detailed for weeks 1-13. Arm B study assessments and radium-223 dosing will continue based on the same schedule detailed for weeks 1-13 up to 6 doses without breaks except for toxicity/intolerance (Section 6.2).

Note: For both arms: Immune studies will follow the schedule detailed in footnote M*

S: End of Treatment visit should occur within 30 days after last study treatment.

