13.9 Analysis of Exploratory Clinical Endpoints

The endpoints will be summarized descriptively and graphically by treatment assignment. Tests for intra-patient changes in values while on combination treatment will use Wilcoxon signed-rank for continuous endpoints; categorical endpoints at two timepoints will be cross-tabulated and relevant proportions will be reported with confidence intervals. Changes in values will also be compared between treatment groups using the Wilcoxon rank sum tests for continuous endpoints. The Kaplan-Meier method will be employed to characterize the distributions of time to event endpoints.

Specifically,

Time to PSA progression: the distributions of time to PSA progression will be summarized using Kaplan-Meier according to treatment arms. Median times to PSA progression will be presented with two-sided 95% confidence intervals.

PSA response: the proportion of patients with a PSA response will be presented with a two-sided 95% confidence interval **(CI)** using exact binominal method according to the treatment arms. Change in PSA will also be summarized descriptively according to the treatment arms and the changes in PSA will also be compared between treatment groups using the Wilcoxon rank sum tests.

Symptomatic skeletal events (SSEs): the proportion of patients with SSEs will be presented with a two-sided 95% confidence interval (CI) using exact binominal method and the distributions of time to first SSEs will be summarized using Kaplan-Meier plots according to the treatment arms.

Quality of life: descriptive statistics at each time point and changes over time will be provided for quality of life, pain and analgesic use measures. Mixed models may be used to explore the impact of time on quality of life and pain adjusting for treatment arms and other relevant factors.

Time to introduction of analgesic use will be summarized using Kaplan-Meier plots according to the treatment arms.

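### The two time-to-alkaline-phosphatase endpoints compare arms whose blood is drawn on different schedules, which by itself makes Arm A reach an event sooner

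*Combined protocol and SAP*

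**What the plan says.** Section 13.1 places two ALP endpoints among the exploratory clinical endpoints: time to normalization, and "Time to decrease in alkaline phosphatase (if initially elevated"). The entry gives no size of fall and no confirmation rule. It does not say which baseline applies (the calendar has chemistry both pre-study and at week 1), what counts as initially elevated, which visits are used, or when patients are censored. The same list is more exact for PSA: "PSA response: defined as decline ≥50% from baseline to 12 weeks of therapy", with a confirming value at least 3 weeks later.

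Section 13.9 has no paragraph on ALP. Its general rule applies: "The Kaplan-Meier method will be employed to characterize the distributions of time to event endpoints", shown by treatment arm. It names no test for these endpoints.

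ALP is part of the chemistry panel (Section 10, footnote E): "Liver function tests to include AST, ALT, total bilirubin and direct bilirubin, alkaline phosphatase". Every chemistry draw is therefore an ALP value. The calendar has chemistry for both arms at weeks 1, 5, 9 and 13, and for Arm A alone at three further visits, weeks 4, 7 and 10; the last column is headed "Wk 10 (Arm A only".

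After week 13 (footnote R), Arm A patients on pembrolizumab alone follow a 3-weekly pattern ("e.g., visits, labs, assessments every 3 weeks only"). For the control arm, "Arm B study assessments and radium-223 dosing will continue based on the same schedule detailed for weeks 1-13 up to 6 doses". Footnote S adds: "End of Treatment visit should occur within 30 days after last study treatment".

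**The concern.** An event of this kind can be recorded only at a blood draw. The arm that is drawn earlier and more often has more chances to show a low value and shows a true fall sooner. Here the difference in schedule is built into the arms, because the extra Arm A visits are pembrolizumab visits. Two Kaplan-Meier curves placed side by side would then separate in favour of the combination even if pembrolizumab did nothing to ALP. The missing definition of a decrease makes this worse, since the literal reading lets ordinary fluctuation count as an event.

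**Working it through.** The documents give no rate, event count or power for either ALP endpoint, so there is no stated figure to reproduce.

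**Inputs from the documents.** Post-baseline ALP draws to week 13 (Section 10):
- Arm A: weeks 4, 5, 7, 9, 10, 13, so k = 6.
- Arm B: weeks 5, 9, 13, so k = 3.

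To about week 25, Arm A on the radium-223 break adds weeks 16, 19, 22 and 25 (k = 10). Arm B adds weeks 17 and 21 and an End of Treatment draw, assumed here at week 25 (k = 6). The ratio of draws is 2.0 to week 13 and 10/6 = 1.67 to week 25.

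**Assumption not in the documents.** Within-patient ALP variation: 10% to 20%. Step 1 does not need it.

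**Step 1: flat ALP, independent noise, any value below baseline counts.** Baseline and the k later values are exchangeable. Baseline is the lowest of the k + 1 values with probability 1/(k + 1), so P(at least one later value below baseline) = k/(k + 1).

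| By | Arm A | Arm B |
|---|---|---|
| Week 5 | 2/3 = 67% | 1/2 = 50% |
| Week 13 | 6/7 = 86% | 3/4 = 75% |
| Week 25 | 10/11 = 91% | 6/7 = 86% |

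**Step 2: other ALP courses, the same in both arms, by week 13.**

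| Course | Arm A | Arm B |
|---|---|---|
| Flat, baseline selected as elevated (variation 15%, between-patient log SD 0.6; simulated) | 89% | 80% |
| Symmetric random walk, 1 − C(2k,k)/4^k | 1 − 924/4096 = 77% | 1 − 20/64 = 69% |
| Rising 1% per week (variation 15%; simulated) | 76% | 61% |
| Rising 3% per week (variation 15%; simulated) | 53% | 34% |
| Rising 3% per week (variation 10%; simulated) | 39% | 22% |
| Falling 3% per week (variation 10%, elevated baseline; simulated) | 100.0% | 99.9% |

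In the falling case the proportions meet, but the median is week 4 in Arm A and week 5 in Arm B: each arm's first draw.

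**Step 3: time to normalization.** With flat ALP, variation 10% and no difference between arms, a simulation gave 14% in Arm A and 11% in Arm B by week 13. The gap has the same direction and is smaller. Its size depends on how far above normal the patients start, which is assumed.

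**Step 4: does a threshold cure it?** Take a 30% fall purely as an illustration (flat ALP, variation 15%). By week 13 the rates are 17% against 11% unconfirmed, and 3% against 2% if confirmed at the next draw. The level drops, but the direction remains.

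**Step 5: shared visits only.** With weeks 5, 9 and 13 in both arms, k = 3 in each, so the any-fall rate is 3/4 = 75% in both and the dates coincide.

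**The case against.** Several stronger readings are tempting, and the documents do not support them.

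- *The plan counts any fall.* It does not say so. It leaves the term undefined, and any fall is only the literal reading.
- *About 9 in 10 patients would reach the event with no treatment effect.* That needs flat, independent ALP values and about 25 weeks of follow-up, where the 2:1 pooled figure is (2 × 10/11 + 6/7)/3 = 89%. By week 13 the pooled figure is (2 × 6/7 + 3/4)/3 = 82%. ALP is also unlikely to be flat: Section 2.2.1 reports median times to ALP increase of 7.4 months on radium-223 and 3.8 on placebo, and normalization in 34% and 1%. Both arms here receive radium-223, so the relevant null is no difference between arms, not no effect on ALP.
- *Arm A has twice as many draws.* This holds to week 13 only. The ratio is 1.67 by about week 25 and changes again later, since pembrolizumab can run to 24 months (Section 5.4) while Arm B sampling ends with its treatment.
- *The between-arm test will have an inflated error rate.* No test is planned for these endpoints. Section 13.11 names a log-rank test for the DNA-repair mutation groups, so rejection rates for a comparison by arm have no place here.

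It is also fair to say that these are two lines in an exploratory list, absent from the objectives in Section 1.4, which drive no decision and apply to a subset of 45 patients. All of this stands and limits the weight of the point. It does not answer the point itself: the schedules differ by arm, the curves are to be shown by arm, and no rule aligns them.

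**Conclusion.** The concern holds in limited form. For both ALP endpoints the planned by-arm curves mix any treatment effect with a difference in sampling. On a literal any-fall reading, Arm A was earlier in every course examined, and more frequent except where ALP falls steadily and nearly everyone has the event. The reference size is 86% against 75% by week 13; it rests on flat ALP and independent noise, and the level shifts widely under other courses. The bias in time to normalization is smaller (14% against 11% under the assumptions stated). The draw counts come from the documents, whereas the variation and trends are assumptions. The consequence is a possible misreading of two descriptive, exploratory summaries. The trial's primary and secondary conclusions are not affected.

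**What to change.** In Sections 13.1 and 13.9, for both ALP endpoints:

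1. Use only the scheduled visits that both arms share, weeks 5, 9 and 13. Ignore the Arm A draws at weeks 4, 7 and 10, and censor both arms at week 13.
2. If later data are wanted, map each arm's values to common windows around Arm B's visits, one value per window. Extending a 4-weekly list of shared visits would not work: Arm A patients on the radium-223 break are drawn at weeks 16, 19 and 22, and Arm B at weeks 17 and 21. Windows also help Arm A patients who stop radium-223 early and move to 3-weekly visits, since they may lack draws at weeks 5 and 9.
3. Define a decrease as a prespecified percentage fall chosen by the sponsor. The documents support no particular figure for ALP.
4. State the confirmation rule: the next available draw in each arm's own schedule, or none for a fall first seen at week 13, where no prompt shared visit follows.
5. State which baseline value applies and what counts as initially elevated.

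The cost is wording only, with no added blood draws and no change to safety monitoring. The downside is that some Arm A values, and any events after week 13, are not used for these two endpoints. If confirmation uses each arm's own draws, a small imbalance returns, because Arm A confirms on separate draws while Arm B reuses its shared visits. With flat ALP and any confirmed fall at the shared visits, a week-13 fall being confirmed at week 16 or 17, the rates are 1 − (3/5 − 1/7) = 54% in Arm A and 1 − (1/5 + 1/5 + 1/10) = 50% in Arm B. Confirming week 5 and week 9 falls at the next shared visit, with none required at week 13, avoids it.

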11. MEASUREMENT OF EFFECT

11.1 Antitumor Effect – Solid Tumors

For the purposes of this study, participants should be re-evaluated for response every 12 weeks (\pm 7 days). In addition to a baseline scan, confirmatory scans should also be obtained 12 (not less than 6) weeks following initial documentation of progressive disease.

Response and progression will be evaluated in this study using the new international criteria proposed by the Response Evaluation Criteria in Solid Tumors (RECIST) guideline (version $1.1)^{52}$ and PCWG2²³.

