11.1.4 Evaluation of Bone Lesions

Existing bone metastases will be the only lesions in some patients. Because bone lesions are notoriously difficult to follow, 'progression' in non-target lesions is defined as the appearance of ≥2 new lesions, and, for the first reassessment only, a confirmatory scan performed 6 or more weeks later is required that shows a minimum of 2 or more additional new lesions (PCWG2 criteria).

Complete Response (CR): Disappearance of all non-target lesions and normalization of PSA. All lymph nodes must be non-pathological in size (<10 mm short axis).

Non-CR/Non-PD: Persistence of one or more non-target lesion(s) and/or maintenance of tumor marker level above the normal limits.

Progressive Disease (PD): Appearance of one or more new lesions and/or *unequivocal progression* of existing non-target lesions. It must be representative of overall disease status change, not a single lesion increase.

Although a clear progression of "non-target" lesions only is exceptional, the opinion of the treating physician should prevail in such circumstances, and the progression status should be confirmed at a later time by the review panel (or Principal Investigator).

Definitions of Progression:

1. Bone Progression:

Appearance of 2 or more new lesions on bone scan, and, for the first reassessment only, a confirmatory scan performed 6 or more weeks later that shows a minimum of 2 or more additional new lesions. The date of progression is the date of the first scan that shows the change.

2. Soft Tissue Progression:

Soft tissue disease progression by modified RECIST v1.1 with additional requirement that progression at first assessment be confirmed by a second scan 6 or more weeks later. Note that for some treatments, a lesion may increase in size before it decreases.

3. Symptomatic Progression:

Symptomatic progression is defined as evidence of unequivocal symptomatic or clinical progression defined by at least 1 of the following:

- A marked escalation in cancer-related pain that is assessed by the Investigator to indicate the need for other systemic therapy or palliative radiotherapy. Ignore early changes (≤ 12 weeks) in pain or health-related quality of life in absence of compelling evidence of disease progression. Confirm progression of pain or health-related quality of life ≥ 3 weeks later

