11.1.5 Evaluation of New Lesions

The finding of a new lesion should be unequivocal (i.e. not due to difference in scanning technique, imaging modality, or findings thought to represent something other than tumor (for example, some 'new' bone lesions may be simply healing or flare of pre-existing lesions). However, a lesion identified on a follow-up scan in an anatomical location that was not scanned at baseline is considered new and will indicate PD. If a new lesion is equivocal (because of small size etc.), follow-up evaluation will clarify if it truly represents new disease and if PD is confirmed, progression should be declared using the date of the initial scan on which the lesion was discovered.

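### The exploratory genomic PFS uses a different progression rule from the secondary PFS, so the same scans can give an event in one and not in the other

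*Combined protocol and SAP*

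**What the plan says.** **Genomic PFS (13.1, Genomic-based endpoints).** Time runs from randomization. The bone component is "Appearance of 2 or more new bony lesions compared to baseline, confirmed on a repeat bone scan ≥6 weeks later". The soft-tissue component is a new lesion, or RECIST 1.1 progression of an existing one, with no confirmation. Section 13.11, which analyses this endpoint, gives no other definition.

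**Secondary PFS (13.1, Secondary Endpoints).** Time runs from the first dose. Progression is "defined by Response Evaluation Criteria in Solid Tumors (RECIST version 1.1) and PCWG2] or death due to any cause".

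**Progression definitions (11.1.4).** At later scans, at least two new bone lesions are enough. When they are found at the first reassessment, they must be backed by "a confirmatory scan performed 6 or more weeks later that shows a minimum of 2 or more additional new lesions". The section labels this rule PCWG2 and dates progression to the first scan showing the change. Soft-tissue progression at the first assessment also needs a second scan at least 6 weeks later.

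**Related text.** Section 11.1.5 cautions that "some 'new' bone lesions may be simply healing or flare of pre-existing lesions". Under 11.1, "participants should be re-evaluated for response every 12 weeks", so the first reassessment falls at about week 12. Section 11.1.8 starts PFS at randomization (or registration).

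**The concern.** Section 11.1.6 describes every patient as having non-measurable, bone-only disease, so the bone clause is likely to decide most radiographic events. In 11.1.4 the demand for further new lesions is the objective guard against reading a flare at the first reassessment as progression. The genomic definition leaves it out and compares with baseline. Neither 13.1 nor 13.11 says that the difference is intended.

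Three things are at stake:

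- PFS by DDR status and PFS by arm would come from event lists that disagree for some patients.
- False events at week 12 that fell equally on both DDR groups would pull the hazard ratio toward 1. This comparison has its own power statement (13.11, Table 21).
- The landmark analysis in 13.11 keeps only patients with no PFS event by 13 weeks. If it uses the genomic definition and dates progression to the first scan, a patient with persisting flare at week 12 is excluded from it.

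**Working it through.** **1. The two rules applied to the same scans**

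| Finding | 11.1.4 (secondary PFS) | Genomic PFS, plain reading |
|---|---|---|
| Two new bone lesions at week 12; repeat scan shows the same two only | No confirmed week-12 event (0 further lesions, 2 needed) | Event |
| Two new bone lesions at week 12; gone on the repeat scan | No event | No event |
| Two new bone lesions at week 12; two further on the repeat scan | Event | Event |
| Two new bone lesions first seen at a later scan, e.g. week 24 | Event, no confirmation needed | Event only if confirmed |
| Soft-tissue progression at first assessment | Needs a second scan | Event without a second scan |

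The genomic bone rule is therefore looser at the first reassessment and stricter afterwards. The time origins differ little if the protocol is followed, because Section 5.1 has treatment start within 7 days of randomization.

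**2. The plan's power figure.** Inputs from 13.11 and Table 21: 36 events, hazard ratio 0.50, 30% DDR prevalence, log-rank test, one-sided alpha 0.15.

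- Schoenfeld formula: z(power) = √(events × p × (1 − p)) × |ln HR| − z(0.85)
- √(36 × 0.3 × 0.7) × 0.693 − 1.036 = 2.750 × 0.693 − 1.036 = 0.869
- Power = Φ(0.869) = 80.8%, so the stated 80% reproduces.

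The formula does not contain the bone-scan rule, so no documented figure changes when the definitions are aligned. The effect of flare can only be illustrated.

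**3. False events at week 12 (assumed rates).** Take 40 patients, 12 mutated and 28 not, with exponential PFS and medians of 12 and 6 months. Week 12 is 12 / 4.345 = 2.76 months.

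- Event-free at week 12: 28 × 2^(−2.76/6) + 12 × 2^(−2.76/12) = 20.4 + 10.2 = 30.6 patients.
- Persisting flare in 10%, 20% or 30% of these gives about 3, 6 or 9 false events.

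**4. Power with persisting flare counted as an event (one-sided 0.15, equal flare in both groups)**

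| Persisting flare | Simulation A | Simulation B |
|---|---|---|
| Not counted | 79–81% | 77% |
| 10% | 76% | 72% |
| 20% | 68% | 65% |
| 30% | 65% | 59% |

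Simulation A rounds progression up to the next 12-week scan and follows patients for 36 months (3,000 trials per rate). Simulation B uses continuous times and analyses at the 36th event (20,000 trials per rate). Each column should be read against its own first row.

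**The case against.** The strongest reply is that the genomic clause is shorthand. It does not define confirmation or mention persistence, and 11.1.4 sets out study-wide what a confirmatory bone scan must show. Section 11.1.5 requires new lesions to be unequivocal, and 11.1.3 sends all scans to central review for the final response analysis. Recognised flare might therefore be excluded anyway. This stands as a possible intention. But the clause names baseline as its comparator and does not refer to 11.1.4, so a programmer or reader could apply either rule. If the 11.1.4 rule was meant, the same edit is needed.

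Other points on that side stand and limit the conclusion:

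- Only flare still visible on the repeat scan counts. Section 11.1 puts the confirmatory scan at 12 weeks, and not less than 6, after first progression, so anywhere from about week 18 to week 24. If half of flares persisted, a 20% flare rate would act like 10%.
- The secondary PFS is not cleanly protected. Section 11.1.4 does not say which scan becomes the reference when first progression is unconfirmed. The same lesions might be counted at a later scan, where no confirmation is needed. The general PD line in 11.1.4 and Table 16 also accept a single new lesion.
- The simulations model only the loosening at week 12, not the stricter rule later. Simulation A also follows patients longer than the 2-year study duration in 13.2.

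A reader might infer that every week-12 flare becomes an event, that the genomic rule is looser throughout, or that the 80% power is lost altogether. The documents support none of these: flare that resolves is an event under neither rule, the direction reverses after the first reassessment, and power falls only under assumed flare rates.

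**Conclusion.** The mismatch is real and nothing in the documents reconciles it. The genomic and secondary PFS differ in bone confirmation, soft-tissue confirmation and time origin. On the plain reading, lesions that appear at week 12 and merely persist are an event in one and not a confirmed week-12 event in the other.

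The size cannot be fixed from the documents. With persisting flare in 10% to 30% of patients, equal in both DDR groups, power would be roughly 59% to 76%, compared with 77% to 81% in the same simulations when flare is not counted. These figures are illustrative. They rest on exponential PFS, the Table 21 medians, the assumed rates, and reading confirmation as persistence.

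The point concerns exploratory genomic analyses. The primary T-cell endpoint is unaffected and the secondary PFS by arm is unchanged. It is worth correcting because the plan makes a power claim for this endpoint and the correction is nearly free.

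**What to change.** In 13.1, replace the bone and soft-tissue clauses of the genomic PFS with a cross-reference to the bone and soft-tissue items under Definitions of Progression in 11.1.4. Cite those items specifically, because the general PD line earlier in that section sets a different threshold. Use one time origin in 11.1.8 and in both PFS definitions in 13.1. State that one PFS dataset serves the analyses by arm, by DDR status and at the week-13 landmark.

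The sponsor should also state which scan is the reference when first progression is not confirmed. Section 11.1.4 is silent on this, so no rule for resetting the reference should be attributed to it.

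If a separate genomic definition is intended, say so, define what confirms a bone lesion, and report how many patients are classified differently.

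The cost is a few lines of text. The same scans are used and the primary endpoint does not change.
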